## 6.3 Concomitant Treatment

### 6.3.1 GVHD During Therapy

If a participant develops new onset GVHD, or experiences an increase in the severity of pre-existing GVHD requiring an escalation of immunosuppressive medication, every effort should be made to continue the study drug without any dose reduction. If the participant is unable to take study drug as a result of GVHD, the study drug can be withheld until the participant is able to resume treatment.

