#### **4.5 Duration of Therapy**

Maintenance therapy will continue for a maximum of 12 cycles (28 days/cycle) from first dose of APR-246, or until one of the following criteria applies:

- Evidence of disease relapse defined as  $\geq 5\%$  blasts for AML patients or  $>5\%$  blasts for MDS patients. Patients who are continuing to derive clinical benefit in the opinion of the investigator may remain on study treatment following relapse.
- Inter-current illness that prevents further administration of treatment.
- Unacceptable AEs.
- Participant decides to withdraw from treatment.
- General or specific changes in the patient's condition render the patient unacceptable for further treatment in the judgment of the investigator.
- Participant begins other treatment for underlying disease (MDS or AML).
- Grade 3-4 acute GVHD or Severe chronic GVHD.

If the participant discontinues treatment early, then the reason for treatment discontinuation and the date the participant was removed will be documented. Participants removed from treatment for unacceptable AEs will be followed until resolution or stabilization of the AE. Participants that discontinue treatment early will continue to be followed for relapse, if not yet documented, and survival.

Patients may continue to receive study treatment in the setting of relapse or progression, up to a maximum of 12 cycles, provided they are continuing to derive benefit in the opinion of the Investigator.

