## **5.2 Post-transplant Criteria for APR-246 and Azacitidine Treatment**

### **5.2.1 Inclusion Criteria**

1. Patient has received one allogeneic transplant for AML or MDS. At time of

treatment, patient must be in morphologic remission for AML or MDS as defined as < 5% blasts for AML and ≤ 5% blasts for MDS, and in cytogenetic remission with no morphologic characteristics of acute leukemia (e.g., Auer Rods) in the BM with no evidence of extramedullary disease such as central nervous system involvement or granulocytic sarcoma. Patients with CR with incomplete count recovery (CRp or CRI) are allowed. Incomplete platelet recovery (CRp) is defined as CR with platelet count < 100 x 10^9/L. Incomplete blood count recovery (CRI) is defined as CR with neutropenia < 1 x 10^9/L with or without complete platelet recovery. Red blood cell count (RBC) and platelet transfusion independence is not required.

2. Any standard (non-study) conditioning [MAC, RIC, or NMA] will be permitted. Acceptable source of allogeneic donor hematopoietic stem cells, as defined per institutional practice (allogeneic HCT for any donor source [matched sibling, URD, mismatched URD, related haploidentical] and any graft source [BM, PB].
3. Patient is ≥ 30 days and ≤ 100 days from hematopoietic cell infusion.
4. Patient is in complete remission after the transplant and has achieved engraftment. Engraftment is defined as ANC≥500/µL and platelets ≥ 20000/µL on 3 consecutive measurements (each occurring at least 1 day apart). The patient must not have had a platelet transfusion within 7 days prior to the first measurement.
5. Patients who have developed grades II-IV acute GVHD will be allowed to initiate maintenance therapy based on the following criteria:
  - Does not require high dose steroids as defined as dosage of > 0.5 mg/kg of prednisone (or equivalent) daily dose within 1 week of post-HSCT screening
  - No escalation of systemic immunosuppression in terms of increase of corticosteroids or addition of new agent/modality within 2 weeks of post-HSCT screening. Dose adjustments (both increase and decrease) of GVHD preventative medications such as calcineurin inhibitors or sirolimus to achieve therapeutic trough levels, is allowed. Topical skin and topical gastrointestinal steroids are allowed.
6. Females must either:
  - Be of non-childbearing potential
    - postmenopausal (defined as at least 1 year without menses) prior to screening, or

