### **5.3 Withdrawal Criteria**

Protocol therapy will be discontinued at any time if any of the following situations occur:

1. Relapsed disease, unless Investigator believes patient is receiving clinical benefit.
2. The development of toxicity which, in the Investigator's judgment, precludes further therapy.
3. Patient refusal.
4. Lost to follow-up/noncompliance.
5. Intercurrent illness.
6. At the discretion of the Investigator.
7. Pregnancy.
8. Study termination.
9. Initiation of anti-MDS/AML therapy or DLI for purpose of treating MDS/AML.

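### Section 6.3.1 says to continue, or hold and resume, study drug in GVHD without any grade limit, while Section 4.5 and the synopsis end therapy for grade 3-4 acute or severe chronic GVHD

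*Combined protocol and SAP*

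**What the plan says.** **Stopping rule.** Section 4.5 (Duration of Therapy) lets maintenance run for at most 12 cycles "or until one of the following criteria applies". One item on the list is "Grade 3-4 acute GVHD or Severe chronic GVHD". The synopsis, under Duration of treatment, repeats it. The relapse item in the same list lets the investigator keep a benefiting patient on treatment; the GVHD item carries no such exception.

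**GVHD on treatment.** Section 6.3.1 (GVHD During Therapy) opens: "If a participant develops new onset GVHD, or experiences an increase in the severity of pre-existing GVHD requiring an escalation of immunosuppressive medication". In that event, "every effort should be made to continue the study drug without any dose reduction". If GVHD prevents dosing, "the study drug can be withheld until the participant is able to resume treatment". No grade or severity limit is given, and Section 4.5 is not mentioned. Sections 6.3.1.1 and 6.3.1.2 leave GVHD management to institutional guidelines.

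**Neighbouring text.**
- Section 5.3 (Withdrawal Criteria) has a second list, introduced by "Protocol therapy will be discontinued at any time if any of the following situations occur". None of its nine items names GVHD. The closest are investigator-judged toxicity ("The development of toxicity which, in the Investigator's judgment, precludes further therapy"), intercurrent illness and investigator discretion.
- Section 5.2.1, item 5: "Patients who have developed grades II-IV acute GVHD will be allowed to initiate maintenance therapy based on the following criteria". The conditions concern steroid dose and recent escalation of immunosuppression.
- Section 8.1.4 has GVHD reported as an adverse event. Table 5 has an Any Other Toxicity row for grade 3 or 4 events: delay, then reduce by one dose level.

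**The concern.** An investigator whose patient develops GVHD will naturally open the section titled for that situation. Section 6.3.1 does not reveal that Section 4.5 makes certain grades a reason to end therapy. One site could stop a patient whom another keeps on treatment, and each could point to protocol text in support.

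The first stake is patient safety. The second is the data. Safety and tolerability is a primary objective, and acute and chronic GVHD are secondary endpoints. If stopping depends on which section a site follows, then exposure, discontinuation rates and recorded reasons for discontinuation partly reflect site practice. Chronic GVHD has a further problem: under Section 8.1.4 its collection window is counted from the last dose, so the decision to stop also decides how long chronic GVHD is recorded.

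**Working it through.** The plan gives no figure to reproduce here, so the check sets the passages side by side for one test case.

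**Test case.** A patient on treatment develops new grade 3 acute GVHD that needs more immunosuppression. This meets the Section 6.3.1 trigger whether the immunosuppression qualifier is read as applying to worsening GVHD only or to new-onset GVHD as well.

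| Text | What follows for this patient |
|---|---|
| Section 4.5 and synopsis | Therapy ends; no exception |
| Section 6.3.1 | Continue without dose reduction; if unable to take the drug, hold and resume |
| Section 5.3 | No GVHD item; left to judgment under toxicity, intercurrent illness or discretion |
| Table 5, Any Other Toxicity, if it applies | Delay, then reduce by one dose level |

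1. *Rows 1 and 2 cannot both be followed.* Continuing, or holding with a view to resuming, is not ending therapy. The same holds for severe chronic GVHD, since Section 6.3.1 does not separate acute from chronic disease or one grade from another.
2. *Row 3 is silence.* Section 5.3 does not tell a site to continue, and it does not say that its list is complete. It contains pregnancy and study termination, which Section 4.5 lacks; Section 4.5 contains GVHD, which Section 5.3 lacks.
3. *Row 4 is uncertain.* GVHD is reported as an adverse event, so the row could be read to cover it. But Table 5 uses CTCAE grades, whereas Section 8.1.4 grades GVHD by Appendices C and D. The protocol does not say whether the row applies.
4. *Entry.* Section 5.2.1 governs starting treatment, and its wording can refer to past GVHD. It meets Section 4.5 only if grade III-IV acute GVHD is still present at entry within the steroid and immunosuppression conditions. It does not require the grade to have fallen below III, and nothing says how Section 4.5 then applies.

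**Effect on the chronic GVHD window.** This illustration uses the protocol's own schedule, assumes no cycle delays, and counts the first dose as Day 1. The last azacitidine dose of cycle *k* falls on Day 28 × (*k* − 1) + 5, and collection ends 30 days later.
- Twelve cycles: 28 × 11 + 5 = Day 313; 313 + 30 = Day 343.
- Therapy ended after cycle 3: 28 × 2 + 5 = Day 61; 61 + 30 = Day 91.
- Difference: 343 − 91 = 252 days.

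Cycle 3 is only an example. After the window closes, Section 7.5 has sites report GVHD results only if they assess it as standard of care, and only until relapse is documented.

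**The case against.** The strongest reply is that the texts can be read together. Section 4.5 is specific and graded, appears identically in the synopsis, and has no benefit exception. Section 6.3.1 is general guidance under concomitant treatment, worded as an effort to be made. On that reading it covers GVHD only until a Section 4.5 criterion is met. The reading is possible, but Section 6.3.1 contains no such limit and a site must supply it. The reply therefore shows that divergence is not certain; it does not remove the conflict in the wording.

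Some text after Section 6.3.1.2 is blacked out. The table of contents places Sections 6.3.2 and 6.3.3 (CNS toxicity and infection) there, so a GVHD reconciliation in that gap is unlikely, though it cannot be excluded.

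Several stronger inferences are tempting, and the documents do not support them:
- *That Sections 4.5, 5.2.1, 5.3 and 6.3.1 all oppose one another.* Only Section 4.5 (with the synopsis) and Section 6.3.1 do. Section 5.3 omits GVHD, and Section 5.2.1 leaves one entry case open.
- *That Section 6.3.1 keeps patients on full dose.* It rules out a reduction because of GVHD. A patient already reduced would stay at the current level.
- *That ascertainment of non-relapse mortality is lost when treatment stops.* Section 4.5 keeps such patients in follow-up for relapse and survival, and Section 7.5 applies survival calls to all patients. Section 8.1.4 also follows acute GVHD until it resolves or no further improvement is expected.

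**Conclusion.** The plan is wrong as written on this point. For a patient who develops grade 3-4 acute or severe chronic GVHD on treatment, Section 4.5 and the synopsis end therapy, while Section 6.3.1 says to continue without reduction or to hold and resume. Following Section 6.3.1 literally breaches Section 4.5. Section 5.3, Table 5 and Section 5.2.1 item 5 add uncertainty but do not themselves contradict Section 4.5.

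This rests on the wording alone and on the blacked-out text containing no reconciliation. The consequences are for patient safety, exposure, reasons for discontinuation and chronic GVHD ascertainment. They arise only if sites in fact act differently, which the documents cannot show.

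The number of patients affected cannot be derived. A reader might assume, say, a 10-20% incidence of these GVHD grades and get 0.10 × 31 = 3.1 to 0.20 × 31 = 6.2 patients. The documents give no basis for that rate. Even if it were right, it would count patients who meet the conflicting text, not patients handled differently.

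**What to change.** The clinical team should:
- reconcile Section 4.5, the synopsis (Duration of treatment) and Section 6.3.1 into one instruction, set out by acute GVHD grade and chronic GVHD severity;
- state whether the Any Other Toxicity row of Table 5 applies to GVHD and, if so, on which grading scale;
- state how the instruction applies to GVHD already present at entry under Section 5.2.1 item 5;
- cross-refer to the single instruction from Sections 5.3 and 6.3.1.

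The cost is protocol wording in an amendment; sample size, visits and the analysis method are unchanged. No view is taken on which clinical rule is right.

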### **6.3.1.1 Management of Acute GVHD**

Acute GVHD should be managed per institutional guidelines. Therapies considered standard are allowed and use of investigational therapy while on study drug is not allowed.

### **6.3.1.2 Management of Chronic GVHD**

Chronic GVHD should be managed per institutional guidelines. Therapies considered standard are allowed and use of investigational therapy while on treatment is not allowed.

[REDACTED]

[REDACTED]  
[REDACTED]  
[REDACTED]  
[REDACTED]

[REDACTED]

As

[REDACTED]  
[REDACTED]  
[REDACTED]  
[REDACTED]  
[REDACTED]  
[REDACTED]

The following recommendations were taken from [National Comprehensive Cancer Network Guidelines for Prevention and Treatment of Cancer-Related Infections \(Version 1.2021\)](#).

**Table 6. Recommendations for prevention and treatment of cancer-related infections**

Organism	Recommendations
Bacterial	Consider fluoroquinolone or other suitable anti-bacterial prophylaxis during neutropenia

Fungal	Consider prophylaxis during neutropenia and for anticipated mucositis. Assess risk for Pneumocystis jirovecii pneumonia and select agent(s) as clinically indicated.
Viral	Start treatment with anti-viral medication in the setting of neutropenia and continually assess the risk for viral infection during treatment with anti-cancer therapy.

Refer to Section 6.2 for guidance on APR-246 dose modification in the setting severe infection and/or infestation event, using the parameter titled, "Any Other Toxicity" (Table 5).

Refer to Section 6.3 for a description of drugs that are not allowed to be used while a patient is on study treatment.

### **6.3.4 Management of Neutropenia with or without Fever**

Monitor complete blood counts at the time of study enrollment and throughout the course of study treatment. Supportive measures such as antimicrobials for prophylaxis or in the setting of prolonged myelosuppression, and/or at the first signs of infection are recommended to reduce the risk of a serious or severe infection that may lead to a fatal outcome in the setting of neutropenia with or without fever (see Section 6.3.3).

Myeloid growth factors may be used in the setting of severe or prolonged neutropenia. Refer to Section 6.3 for a description of drugs that are not allowed to be used while a patient is on study treatment.

Refer to Section 6.2.1 for APR-246 dose modification in the setting of severe or life-threatening neutropenia with or without fever.

### **6.3.5 General Concomitant Medications and Supportive Care Guidelines**

#### **6.3.5.1 Antimicrobials**

Antibacterial, antiviral and antifungal prophylaxis and treatment during and after allogeneic HSCT are recommended and can be administered based on local institutional guidelines.

### **6.3.5.2 Tapering of GVHD Prophylaxis**

Tapering of immunosuppression should be followed per institutional practice in the absence of GVHD. There are no formal recommendations given that participants receiving HCT from any type of donor, after any conditioning and receiving any GVHD prophylaxis regimen are eligible.

### **6.3.5.3 Donor Lymphocyte Infusions**

Pre-emptive/prophylactic administration of donor lymphocytes for disease progression (morphological or molecular) is not permitted in this protocol. DLI for infectious complications or modulation of T cell donor chimerism after allograft administration per institutional guidelines is allowed. For any unresolved questions regarding DLI administration should be discussed with the Medical Monitor.

### **6.3.6 Prohibited Therapy**

- Other anticancer therapy: Anticancer therapy (chemotherapy, endocrine, biologic or radiation therapy, and surgery) other than the study treatments must not be given to patients while the patient is enrolled in the treatment portion of the trial. If such agents are required for a patient then, the patient must be permanently discontinued from the treatment portion of the study. Exception: for breast cancer or prostate patients on adjuvant hormonal therapy (e.g., anastrozole/tamoxifen or leuprolide) who have been disease free for at least 1 year.
- Other investigational therapies: Other investigational therapies must not be used while the patient is on the study including those for disease or GVHD.

### **6.3.7 Other Concomitant Treatment (Medication and Non-medication Therapy)**

In general, the use of any concomitant medications/therapies deemed necessary for the care of the patient are allowed, with specific exceptions below. Prophylactic anti-emetic therapy is permitted where indicated. Participating centers will adhere to institutional practice regarding the monitoring of serum levels of immunosuppressive agents such as tacrolimus or azoles.

Any disease progression that requires other specific anti-tumor therapy will be cause for discontinuation from the trial.

### **6.3.8 Permitted Medications**

#### **6.3.8.1 Growth Factors**

Erythropoiesis-stimulating agents (ESAs) are not allowed for anemia during the study. G-CSF is allowed for evidence of neutropenia.

#### **6.3.8.2 Anticoagulant Therapy**

Subjects who are taking warfarin (or equivalent) may participate in this study; however, it is recommended that prothrombin time (PT-INR) and PTT be monitored carefully at least once per week for the first month, then monthly if the INR is stable. Subcutaneous heparin, low molecular weight heparin and oral anticoagulants are permitted.

#### **6.3.8.3 Blood Products**

The use of blood products to include packed red blood cells (PRBCs) and platelet transfusions are permitted and to be given at the discretion of the treating physician. Recommended guidelines for transfusion include a platelet threshold of 10,000/L for platelet transfusion and a hemoglobin threshold of 8.0g/dL for PRBC transfusion or as clinically deemed by the discretion of treating physician.

### **6.4 Monitoring Subject Compliance**

Study drug will be administered only to eligible patients by the appropriate study personnel. Drug dispensing and administration records will be maintained.

## 7.0 STUDY EVALUATIONS

Unscheduled visits and laboratory monitoring may occur as needed. Window of 3 days applies except where noted.

### 7.1 Pre-Screening

APPENDIX B lists visits and assessments prior to starting APR-246 and azacitidine. Unscheduled visits and laboratory monitoring may occur as needed.

#### 7.1.1 Pre-Screening (Day -28 to -1 prior to HSCT)

- Sign informed consent
- *TP53* mutation confirmation
- Disease assessment: BM aspirate and/or biopsy sample must be collected prior to the start of the pre-transplant conditioning regimen.
- Pregnancy test (women of child-bearing potential only)
- ECGs; see Table 7.

#### 7.1.2 Day 0

- Transplant

#### 7.1.3 Post-Transplant, APR-246 Screening Period (Day 1 to 100)

Post-HSCT evaluation will occur as per institutional standard practices.

APR-246/azacitidine screening period occurs during Day 30 to 100 post-HSCT. The date will vary but should start (Day -28 relative to first dose) as soon as engraftment and the requirements in Section 7.1.4 are confirmed. The first dose must be administered no more than 28 days after confirmation.

The procedures listed below should be performed within 28 days prior to the first dose, or as indicated. Starred (\*) procedures should be done within 3 days prior to the first dose.

- Sign informed consent
- Disease assessment
- Eligibility
- Karnofsky performance status

- Medical history and Transplant Details
- Physical exam with Weight\*
- Vital signs\*
- CBC\*
- CMP\*
- ECGs\*; see Table 7.
- Pregnancy test (women of child-bearing potential only)\*
- Pre-treatment/baseline Bone marrow (BM)/Aspirate (BMA) for correlatives/exploratory: see Table 9
- GVHD monitoring
- Chimerism, immune reconstitution
- Monitor adverse events
- Concomitant medications

#### **7.1.4 Confirmation to Proceed to APR-246 and Azacitidine Treatment (Day 30 to 100)**

- Bone marrow exam, including cytomorphology, cytogenetic assessment, and flow cytometry analysis.
- Engraftment is defined as  $ANC \geq 500/\mu L$  and platelets  $\geq 20000/\mu L$  on 3 consecutive measurements (each occurring at least 1 day apart). The patient must not have had a platelet transfusion within 7 days prior to the first measurement.
- Once this BM biopsy confirms CR and all other eligibility is confirmed, the patient must start APR-246 and azacitidine treatment within 28 days of confirmation.

## **7.2 APR-246 and Azacitidine Treatment**

APPENDIX B lists visits and assessments. Unscheduled visits and laboratory monitoring may occur as needed. The first dose must be administered no more than 28 days after confirmation.

### **7.2.1 Cycle 1, Day 1**

- APR-246 (administered Days 1-4)
- Azacitidine (administered Days 1-5)
- PK sampling Day 1 pre- and post-dosing: see Section 8.4
- ECGs; see Table 7.

- Adverse events
- Concomitant medications

### **7.2.2 Cycle 1, Days 2, 3, 4, 5**

- APR-246 (administered Days 1-4)
- Azacitidine (administered Days 1-5)
- Additional ECG monitoring in select patients; see Section 6.2
- PK sampling predose Day 2: see Section 8.4
- Adverse events
- Concomitant medications

### **7.2.3 Cycle 1, Days 7, 14, 21**

- Vital Signs
- CBC
- CMP
- Adverse events
- Concomitant medications

### **7.2.4 Cycle 1, Day 28**

- Physical exam with Weight
- Vital signs
- CBC
- CMP
- GVHD monitoring
- Adverse events
- Concomitant medications
- Disease assessment (blood)

### **7.2.5 Cycles 2-4, Day 1 (Day 29 of prior cycle)**

First dose of next cycle may be delayed up to 4 weeks.

- APR-246 (administered Days 1-4)
- Azacitidine (administered Days 1-5)
- Physical exam with Weight; Does not need to be repeated if done within 3 days prior
- Vital signs; Does not need to be repeated if done within 3 days prior
- CBC; Does not need to be repeated if done within 3 days prior

- CMP; Does not need to be repeated if done within 3 days prior
- ECGs; see Table 7.
- Adverse events
- Concomitant medications

#### **7.2.6 Cycles 2-4, Days 2, 3, 4, 5**

- APR-246 (administered Days 1-4)
- Azacitidine (administered Days 1-5)
- Additional ECG monitoring in select patients; see Section 6.2
- Adverse events
- Concomitant medications

#### **7.2.7 Cycles 2-4, Day 14**

- CMP
- Adverse events
- Concomitant medications

#### **7.2.8 Cycles 2-4, Day 28**

- Physical exam with Weight
- Vital signs
- CBC
- CMP
- GVHD monitoring
- Adverse events
- Concomitant medications
- Disease assessment, blood every cycle, bone marrow end of Cycle/Month 3
- Chimerism, end of Cycle/Month 3

